12 PROTOCOL VIOLATIONS

A protocol violation occurs when either the subject, and/or the investigator, and/or Eye Pharma fails to adhere to significant protocol requirements affecting the inclusion, exclusion, subject safety and primary endpoint criteria. Protocol violations for this study include, but are not limited to, the following:

- Failure to meet inclusion/exclusion criteria
- Compliance with study product regimen under 90%.

Failure to comply with Good Clinical Practice (GCP) guidelines will also result in a protocol violation. Eye Pharma will determine if a protocol violation will result in withdrawal of a subject.

When a protocol violation occurs, it will be immediately reported by written (via e-mail) to and discussed with the Sponsor. The Sponsor's evaluation results and, request of corrective actions will be reported to the investigator by written (via e-mail).

13 ADVERSE EVENTS REPORTING AND DOCUMENTATION

13.1 Overview

An Adverse Event (AE) is "Any untoward medical occurrence in a patient or clinical investigation patient administered a pharmaceutical product and which does not necessarily have to have a causal relationship with this treatment. An AE can therefore be any unfavorable and unintended sign (including for example an abnormal laboratory finding), symptom, or disease temporally associated with the use of a medicinal product, whether or not considered related to the medicinal product".

This definition includes intercurrent illnesses or injuries, exacerbation of pre-existing conditions, and adverse events occurring as a result of drug withdrawal, abuse, misuse or

overdose. Adverse events observed during all periods of the study are to be recorded, including adverse events occurring during a period without study product intake. This also includes adverse events which are reported within in the screening phase (since the patient has signed Informed Consent Form).

Signs and symptoms considered as lack of efficacy and occurring during the study will not be recorded on the AEs Section of the CRF except on the condition that, in the investigator's opinion, they are caused by any reason different from lack of efficacy of study product or meet the definition of serious AE.

Clinically significant findings at screening (e.g., laboratory findings) are not considered an AE/SAE.

If a clinical significant finding recorded at screening worsens (in terms of severity or frequency) during the study, it must be recorded as an AE/SAE.

Unexpected Adverse Event

An Unexpected Adverse Event is any experience not previously reported (in nature, severity or incidence) in the current package insert for the study product.

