7.1 Allowed Medications and Treatments

All topical drugs (any topical midriatic treatment and any traditional topical therapy for uveitis) will be admitted for the treatment of the signs and symptoms associated with HLA-B27-associated chronic relapsing uveitis.

In the case of relapse with LFM values are > 100 ph/ms despite treatment with topical therapy, or in any case the LFM values result to be > 100 ph/ms, then a systemic therapy is recommended and the subject has to be dropped-out from the study and treated according to the best medical judgement.

7.2 **Prohibited Medications and Treatments**

The following medications are prohibited during the study and the administration will be considered a protocol violation: supplements and nutraceuticals, systemic therapies for uveitis (anti-inflammatory, immunosuppressive, biologicals), hormonal contraceptives, long-term treatment with systemic anti-inflammatory, immunosuppressive or biological drugs for other diseases different from uveitis. Systemic therapies with anti-inflammatory, immunosuppressive drugs are allowed for reasons different from uveitis and in any case for periods not exceeding 15-30 days.

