9.1.4 Physical Examination

A physical examination will be performed by the investigator at baseline visit (t₀). Qualified staff may complete the abbreviated physical exam at all other visits. New abnormal physical exam findings during the study must be documented as adverse event and will be followed by a physician or other qualified staff at the next scheduled visit.

A rheumatologic evaluation will be done at screening in order to assess if the whether the disease also has a systemic involvement (ankylosing spondylitis) or not.

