13.3 Abnormal test findings

An abnormal test finding will be classified as an *adverse effect* if one or more of the following criteria are met:

- The test finding is accompanied by clinical symptoms
- The test finding necessitates additional diagnostic evaluation(s) or medical/surgical intervention; including significant additional concomitant drug or other therapy (Note: simply repeating a test finding, in the absence of any of the other listed criteria, does not constitute an adverse effect.)
- The test finding leads to a change in study dosing or exposure or discontinuation of subject participation in the clinical study
- The test finding is considered an adverse effect by the investigator and /or Eye Pharma

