### **12.2** Adverse Events

Adverse event will be coded using the last updated version of the Medical Dictionary for Regulatory Activities (MedDRA) dictionary to give a preferred term (PT) and a system/organ class term (SOC) for each. Adverse events will be tabulated by treatment group. Tables will be included the number of patients who experienced at least one AE, of study product-related AEs (defined as definitely, probably, possibly, or unrelated), of serious AEs, and the number of patients withdrawn due to AE, summarized by treatment arm. Comparisons between treatment arms will be performed using chi-square test.

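### Protocol 13.1 and 13.3 give different answers on whether a symptomatic relapse is an adverse event, and SAP 12.2 compares AE counts between arms without saying which rule applies

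*Protocol*

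**What the plan says.** **Against recording.** Protocol 13.1 states: "Signs and symptoms considered as lack of efficacy and occurring during the study will not be recorded on the AEs Section of the CRF". It has two exceptions: the investigator's opinion that "they are caused by any reason different from lack of efficacy of study product or meet the definition of serious AE".

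**For recording.** Protocol 13.3 classes an abnormal test finding as an adverse effect if any one of its criteria is met. The first is "The test finding is accompanied by clinical symptoms". The second is a need for further diagnostic work or for medical or surgical intervention, including significant added drug therapy. The third is "The test finding leads to a change in study dosing or exposure or discontinuation of subject participation in the clinical study". None excepts lack of efficacy. The general AE definition in 13.1 also leans this way: "This definition includes intercurrent illnesses or injuries, exacerbation of pre-existing conditions". So does protocol 9.1.4: "New abnormal physical exam findings during the study must be documented as adverse event".

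**What a relapse involves.** Protocol section 2 defines it by anterior chamber cells of grade 1+ or higher, with an alternative when the view is impaired. Section 10.4 adds an unscheduled visit with a full ophthalmic evaluation, and topical or systemic treatment. Under 7.1, LFM above 100 ph/ms means that "the subject has to be dropped-out from the study".

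**How the data are used.** SAP 12.2 tabulates patients with any AE and "the number of patients withdrawn due to AE, summarized by treatment arm", and compares arms by chi-square. SAP section 13, on departures from the protocol analysis, does not mention relapse as an AE.

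**The concern.** Relapse is the primary endpoint and is expected in most patients. Whether it also counts as an AE therefore decides what the any-AE table measures. If relapses are entered, the chi-square test on that table is mostly a coarser second look at efficacy, and non-relapse events contribute little to it. If they are not entered, the table measures other events, as a safety table should. Two sites could each point to protocol text in support of opposite practices, and the pooled count would then mix them. The SAP gives the analyst no rule for separating them.

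**Working it through.** **Step 1: one event, both rules.** Take a non-serious relapse with pain and raised flare, attributed by the investigator to lack of efficacy and treated topically.

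| Text | Application | Result |
|---|---|---|
| Protocol 13.1, exclusion | Lack of efficacy, not serious, no other cause | Not on the AE page |
| Protocol 13.3, first criterion | Abnormal flare with symptoms | Adverse effect |
| Protocol 13.3, second criterion | Full evaluation and treatment under 10.4 | Adverse effect |
| Protocol 13.3, third criterion | Only if LFM exceeds 100 ph/ms, through 7.1 | Adverse effect |
| Protocol 9.1.4 | Only if the sign counts as a physical examination finding | AE |

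Protocol 9.1.4 is the weaker support, because section 10 lists the physical examination apart from the ophthalmic evaluation. The clash between 13.1 and 13.3 does not depend on it.

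**Step 2: the planning figures.** Protocol 14.7 gives 275 relapses in 106 patients before treatment (275/106 = 2.59, stated as 2.6) and 36 after (36/106 = 0.34). The plan assumes 2.0 against 2.6 with SD 0.7. A two-sided 5% t-test with 80% power for 0.6/0.7 = 0.857 needs 22.37, so 23 per arm and 46 in total, as stated. With 20% dropout, 46/0.80 = 57.5, so 58; the plan recruits 60. The planning figures are not in dispute; only the means are used below.

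**Step 3: share with an AE from relapse alone.** If counts are Poisson (the distribution named for the GLMM) and every relapse is entered, the share is 1 − exp(−mean).

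- Active: 1 − exp(−2.0) = 1 − 0.135 = 0.865, or 25.9 of 30.
- Placebo: 1 − exp(−2.6) = 1 − 0.074 = 0.926, or 27.8 of 30.

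**Step 4: range.**

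- *Other AEs.* With an assumed independent non-relapse AE rate b in both arms, the any-AE rate is 1 − (1 − b) × exp(−mean). For b = 0 it is 86.5% against 92.6%; for b = 30%, 90.5% against 94.8%. With relapses excluded it is simply b.
- *Incomplete entry.* If half the patients in each arm are at sites that enter relapses, and b = 0, the shares are 0.5 × 0.865 = 43% and 0.5 × 0.926 = 46%.
- *A much larger effect.* At the earlier study's post-treatment mean of 0.34 on active, 1 − exp(−0.34) = 28.8% against 92.6%. With 30 per arm the any-AE comparison then has power close to 100%, driven by efficacy alone.
- *Less spread than Poisson.* A Poisson count with mean 2.6 has SD √2.6 = 1.61, but the protocol states 0.7. Less spread leaves fewer patients without a relapse, so the placebo share would be nearer 100%.

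**Step 5: withdrawals.** Protocol 11.1 and SAP 9.1.4 list the need for systemic therapy for uveitis as a discontinuation reason separate from adverse event. Protocol 10.4 withdraws patients prescribed it, and 11.2 replaces dropouts who start such therapy, so sites must identify them. SAP 10.1 reports dropouts by reason. One overlap remains: a drop-out triggered by LFM above 100 ph/ms also meets the third criterion of 13.3.

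**Step 6: ocular complications.** IOP, OCT thickness, keratopathy and synechiae are assessed at each scheduled visit and compared between arms under SAP 11.4.2. Under 13.1, serious events and those with another cause are still recorded, as are clinically significant screening findings that worsen. What can be absent from the AE tables is a non-serious complication attributed to lack of efficacy.

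**The case against.** The strongest reply is that 13.1 is a broad definition followed by a specific exclusion, so the definition and the exclusion do not conflict. On this view 13.3 can be followed as well: it speaks of an adverse effect rather than CRF entry, it does not name relapse, and 13.4.1 sends AEs and abnormal findings to the case histories, while 13.1 governs the AE page. That is a workable reading, but no text states this order of precedence and 13.3 carries no exception. It shows what a clarification could say, not that one is unnecessary.

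A second reply is that relapses entered as AEs would be MedDRA-coded and could be separated later. That stands, and the fix uses it. Coding cannot restore AE details for events that were never entered.

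Three stronger readings are tempting and do not hold:

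- *Withdrawals due to AE become relapse counts.* The separate systemic-therapy reason answers most of this; only the LFM-triggered overlap remains.
- *Harm to the eye disappears from the trial.* The complications are measured and compared as secondary endpoints. The gap is confined to the AE tables.
- *A real safety difference would be masked.* With assumed other-AE rates of 30% and 50%, and 2.0 relapses in both arms, the any-AE rates become 1 − 0.70 × 0.135 = 90.5% and 1 − 0.50 × 0.135 = 93.2%, so 20 points shrink to 2.7. The arithmetic is right, but those rates appear in neither document, and every relapse would have to be entered despite 13.1. It shows a direction, not an expected size.

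**Conclusion.** The concern holds as a conflict between stated rules. For a non-serious symptomatic relapse attributed to lack of efficacy, 13.1 says not to record and 13.3 says adverse effect; neither the protocol nor the SAP settles it. The main consequence is for the any-AE comparison. If all relapses are entered, about 86% and 93% of patients have an AE from relapse alone, and the test largely repeats the primary endpoint. This rests on the planning means, a Poisson count and full entry at every site. Partial entry lowers the shares; the stated SD of 0.7 would raise them. The documents do not show how sites actually record relapses, so differing practice is a risk rather than an established fact. For withdrawals and ocular complications, only the narrow gaps in steps 5 and 6 remain.

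**What to change.** **Protocol.** Reconcile 13.1 and 13.3, and align 9.1.4, with one recording rule: a relapse meeting the section 2 definition, with its own findings, goes on the relapse record and not the AE page, unless it is serious or has another cause. This concerns recording only, not patient management.

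**SAP 12.2, before unblinding.**

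- Tabulate and compare the any-AE and withdrawn-due-to-AE counts excluding relapse.
- Identify any relapse already entered as an AE by its MedDRA preferred term, and show it separately.
- Count relapse or LFM-triggered drop-outs under the existing systemic-therapy reason.
- Show new or worsened IOP abnormality, macular edema, keratopathy and synechiae in a separate safety row taken from visit data. Keep them out of the any-AE count unless also reported as AEs; entering them all as AEs would bring the sequelae of relapse back into that count.

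**Cost.** Wording, an eCRF completion note and one extra table row; the relapse and visit data are already collected. Some ocular events will appear in both efficacy and safety tables. SAP 4.2 describes enrolment as complete, so the protocol change may come late, and AE severity and causality cannot be recovered for events never entered. The SAP change is still open, since SAP 4.3 places unblinding after database lock.

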13.2 AE Severity

The international common terminology criteria for Adverse Events should be used to assess and grade AE severity, including laboratory abnormalities judged to be clinically significant. It should be pointed out that the term "severe" is a measure of intensity and that a severe AE is not necessarily serious.

Severity (Toxicity Grade)	Description
Mild (1)	Transient or mild discomfort; no limitation in activity; no medical intervention or therapy required. The subject may be aware of the sign or symptom but tolerates it reasonably well.
Moderate (2)	Mild to moderate limitation in activity, no or minimal medical intervention/therapy required.
Severe (3)	Marked limitation in activity, medical intervention/therapy required hospitalizations possible.
Life-threatening (4)	The subject is at risk of death due to the adverse experience as it occurred. This does not refer to an experience that hypothetically might have caused death if it were more severe.

13.3 Abnormal test findings

An abnormal test finding will be classified as an *adverse effect* if one or more of the following criteria are met:

- The test finding is accompanied by clinical symptoms
- The test finding necessitates additional diagnostic evaluation(s) or medical/surgical intervention; including significant additional concomitant drug or other therapy (Note: simply repeating a test finding, in the absence of any of the other listed criteria, does not constitute an adverse effect.)
- The test finding leads to a change in study dosing or exposure or discontinuation of subject participation in the clinical study
- The test finding is considered an adverse effect by the investigator and /or Eye Pharma

13.4 Events to be reported

13.4.1 All adverse Events

All observed adverse events (serious or non-serious) and abnormal test findings, regardless of the treatment group, or any suspected causal relationship of adverse event to the investigational products will be recorded in the subjects' case histories. For all adverse events, sufficient information will be pursued and/or obtained so as to permit (1) an adequate determination of the outcome of the event (i.e., whether the event should be classified as a serious adverse event) and (2) an assessment of the casual relationship between the adverse event and the investigational treatment. Adverse events or abnormal test findings suspected to be associated with the investigational product will be followed until the event (or its sequelae) or the abnormal test finding resolves or stabilizes at a level acceptable to the sponsor-investigator.

13.4.2 Adverse Events requiring immediate Notification

Serious Adverse Events (SAE)

A serious adverse event (SAE) is any event that suggests a significant hazard, contraindication, side effect, or precaution, whether or not it is considered to be associated with the study product. A SAE is an AE that meets any of the following criteria:

Results in death. This includes any death that occurs during the conduct of a clinical trial, including deaths that appear to be completely unrelated to the study products (e.g., car accident).

- Is life-threatening. This includes any AE during which the patient is, in the view of the investigator, at immediate risk of death from the event as it occurs. This definition does not include events that may have caused death if they had occurred in a more severe form.
- **Requires inpatient hospitalization** or prolongation of existing hospitalization.
- > Results in persistent or significant disability or incapacity.
- > Is a congenital anomaly or birth defect.
- Other medical events that based upon appropriate medical judgment are thought to jeopardize the patient and/or require medical or surgical intervention to prevent one of the outcomes defining a SAE.

Planned hospitalizations scheduled prior to the informed consent but performed during the study should not be considered (serious) AEs.

Serious Adverse Event Reporting

Study sites will document all SAEs that occur (whether or not related to the study product). The collection period for all SAEs will begin after the informed consent is obtained and will finish 2 weeks after the patient has withdrawn study participation (defined as time passed from the last visit). All SAE occurred in that time range must be reported to Eye Pharma within 24 hours of learning about its occurrence:

Contact person for USA: [name] – Eye Pharma US [contact] e-mail: [contact]

Contact person for Italy:

[name] – Eye Pharma S.p.A. [contact] [contact]

e-mail: [contact]

In accordance with the standard operating procedures and policies of the local Institutional Review Board (IRB)/Independent Ethics Committee (IEC), the site investigator will report SAEs to the IRB/IEC.

The sponsor will be responsible for reporting to Competent Authorities, according to local laws and regulations.

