8.3.3 Packaging and Labeling

Packaging: study product and placebo will be supplied in cartons containing 30 single foil pouches that are enough for a month-long treatment.

The study products will be delivered to the subjects based on the interval period between visits as indicated below:

Visit 1 (baseline, t₀): each patient receives 13 kits containing 30 single foil pouches

Visit 2 (t₁, 6 months): each patient receives 18 kits containing 30 single foil pouches.

Labeling: Each carton (kit) of study products will be labeled with the protocol number, a

treatment number, production lot, expiration date, the name of the sponsor, and directions for patient use and storage.

8.4 **Supply of Study Products at the Site**

Eye Pharma (or designee) will ship the Study Products to the investigational sites after sites activation (i.e. all required regulatory documentation has been received by Eye Pharma and a contract has been executed).

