8.4.1 Dosage/Dosage Regimen

Study products will be administered as follows.

Two single foil pouches per day, each with main meals, with an estimated interval of about 8 hours between doses. A minimum interval of 4 hours between doses should be maintained.

The treatment will last for a period of 12 months.

Table 3 - Dosage	Regimen
------------------	---------

	Dosage regimen/ Each center	Administration	Minimum interval between doses	Duration
NORFLO [®] ORO	3.49 gr (2 single foil pouches of 1.7450 g) per day	Each single pouch (1.7450 g) at main meal in a glass of water	4 hr	12 months
PLACEBO	3.49 gr (2 single foil pouches of 1.7450 g) per day	Each single pouch (1.7450 g) at main meal in a glass of water	4 hr	12 months

8.4.2 **Dispensing**

Investigator (or designee) delivers the study product to the patient at each visit.

8.5 **Supply of Study Product at the Site**

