10.4 Additional Unscheduled Visits in Case of Relapse

Should a relapse occur, an unscheduled visit will be performed including a complete ophthalmic evaluation. The number of cells in the AC will be determined by slit lamp, too.

Topical or systemic treatment will be prescribed to the subject according to the severity of the relapse and according to the best medical judgement.

Two following visits will be scheduled 2 and 6 weeks thereafter. During these visits a complete ophthalmic evaluation will be done.

If the subject is prescribed a systemic treatment for the relapse, he/she will be withdrawn from the study, and treated according to the best medical judgement.

If only topical treatments are prescribed, the subject will be allowed to continue the study. Depending on the onset time of the relapse it could be necessary to delay Visit 2 or Visit 3 around 2 months after the topical treatment conclusion.

Should Visit 2 be delayed, the delay will be recovered by keeping the date of Visit 3 at 12 months.

Should Visit 3 be delayed, the delay will not be recovered.

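### The SAE collection window runs from the last visit, not the last dose, so it can close while a patient who left without a closing visit is still dosing, and before most births after an exposed pregnancy

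*Protocol*

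**What the plan says.** **Window.** Protocol section 13.4.2 opens SAE collection at consent and says that it "will finish 2 weeks after the patient has withdrawn study participation (defined as time passed from the last visit". The duty to report to the sponsor within 24 hours covers SAEs that occur in that range. The SAE criteria in the same section include "Is a congenital anomaly or birth defect". The SAP sets no SAE window of its own.

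**Visits and product.** Clinic visits are at baseline, 6 and 12 months, with 10 days' tolerance at the last two (Appendix 1). One phone call at about 3 months checks product intake (10.1). Under section 8.3.3, at Visit 1 "each patient receives 13 kits containing 30 single foil pouches" and at Visit 2 "each patient receives 18 kits containing 30 single foil pouches". Section 8.4.1 sets the daily use: "Two single foil pouches per day, each with main meals".

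**Leaving early.** Section 10.5 asks for the Visit 3 activities at early withdrawal, where feasible, and these include taking back product (10.3). Section 11.1 asks patients who stop treatment to attend a discontinuation visit and encourages them to keep the remaining visits. Its list of reasons for stopping includes loss to follow-up and pregnancy.

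**Relapse.** Section 10.4 says "Two following visits will be scheduled 2 and 6 weeks thereafter". It also withdraws from the study any patient who is given systemic treatment for the relapse.

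**The concern.** A post-treatment SAE window is meant to cover the time on product plus a short tail. This one is tied neither to the last dose nor to the withdrawal date, but to the last visit, and planned visits are six months apart. Three situations that the protocol itself foresees fit it badly:

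1. A patient lost between visits has Visit 1 or Visit 2 as the last visit, yet took home months of product.
2. A patient withdrawn at a relapse may or may not return at weeks 2 and 6, and nothing says whether those visits move the end of the window.
3. A pregnancy stops treatment, and a birth defect is an SAE, but no section describes follow-up to birth. Hormonal contraceptives are prohibited (6.3, 7.2), and pregnancy is tested only at visits (9.1.5).

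At stake are the completeness of SAE reporting during exposure and its consistency between sites.

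**Working it through.** The two weeks are a stated rule, so there is no plan figure to reproduce. The check is date arithmetic: window end = last visit + 14 days, compared with planned dosing, product supply, the relapse visits and birth.

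**Supply.** Days = kits × 30 pouches ÷ 2 per day.
- Visit 1: 13 × 30 ÷ 2 = 195 days.
- Visit 2: 18 × 30 ÷ 2 = 270 days. Treatment lasts 12 months, so planned dosing after Visit 2 is only 365.25 ÷ 2 ≈ 183 days. The 270 days are a ceiling on supply, not planned exposure.
- Section 8.3.3 also describes "cartons containing 30 single foil pouches that are enough for a month-long treatment". At two pouches a day a carton lasts 30 ÷ 2 = 15 days. Sections 8.3.3 and 8.4.1 must be reconciled. The figures here use the two-a-day statement.

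**Patient who leaves between visits with no closing visit.** The window closes on day 14 after Visit 1 or Visit 2.
- To the next planned visit: 182.6 − 14 ≈ 169 days uncovered, or 192.6 − 14 ≈ 179 to its late limit.
- After Visit 1, to the end of supply: 195 − 14 = 181 days at most.
- After Visit 2, to the end of planned treatment: 183 − 14 = 169 days.
- Number affected: the dropout allowance is 20% of 60 = 12. The share leaving without a closing visit is not given, so the range is 0 to 12, which is a bound and not an estimate.

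**Completer, or patient who attends a withdrawal visit.** Product is collected and the window runs 14 days beyond that visit. There is no overlap with dosing.

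**Patient withdrawn at a relapse (relapse visit = day 0, follow-up on days 14 and 42).**

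| Visit taken as last | Window ends | Relative to the week-6 visit |
|---|---|---|
| Relapse visit | day 14 | 28 days before |
| Week 2 | day 14 + 14 = 28 | 14 days before |
| Week 6 | day 42 + 14 = 56 | 14 days after |

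This path is foreseeable. Section 7.1 drops patients with flare above 100 ph/ms, and section 2 cites a mean initial flare of 160 ph/ms in acute HLA-B27 episodes.

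**Exposed pregnancy.** The documents give no gestation length. I assume 266 days from conception, with a range of 238 to 280.
- Patient who stays to Visit 3 on day 365: the window ends on day 379. The latest conception with a birth inside it is 379 − 266 = day 113 (379 − 280 = day 99; 379 − 238 = day 141).
- If conceptions were spread evenly over the year, 113 ÷ 365 ≈ 31% would be covered (99 ÷ 365 ≈ 27%; 141 ÷ 365 ≈ 39%).
- Pregnancy found at Visit 2, patient leaves then: the window ends at 182.6 + 14 ≈ day 197. Even for conception on day 0, birth comes 238 − 196.6 ≈ 41 to 266 − 196.6 ≈ 69 days later (gestation 238 to 266 days).

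**The case against.** The strongest reply is that the clock starts only at withdrawal, so a continuing participant is covered throughout. Sections 10.5 and 11.1 ask anyone who leaves to attend a visit at which product is taken back. This stands, and it rules out the reading that the window closes between routine visits. But both sections depend on the patient attending, so they do not help with the patient who does not come back.

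A reader might infer several stronger points that the documents do not support:
- **256 days of uncovered dosing after Visit 2 (270 − 14).** This counts all the product supplied and runs past the 12-month treatment period.
- **Four of six relapse follow-up weeks lost.** This holds only if the relapse visit is the last visit. The text leaves that open, and also whether the follow-up visits continue after withdrawal.
- **No birth outcome is ever captured.** Births from early conceptions fall inside the window if the patient stays to Visit 3, as section 11.1 encourages.
- **A contradiction with section 13.1.** That section says "Adverse events observed during all periods of the study are to be recorded", including periods off product. It describes what is recorded during the study, whereas 13.4.2 sets how long collection lasts after withdrawal. The two can stand together.
- **These patients are the likeliest to have serious events, or their events drop out of the comparison between arms.** Nothing shows the first. SAP section 12.2 tabulates SAEs by arm without a window restriction.

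Section 13.4.1 does follow events suspected to be product-related until they resolve or stabilize, but it sets no new SAE collection period. It is also fair to say that rewording cannot recover data from a patient who cannot be reached.

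**Conclusion.** The point holds in a limited form. The rule is sound for completers and for anyone who attends a closing visit. For a patient who leaves between visits without one, it ends SAE collection about 169 days before the next planned visit while dosing may continue. For a relapse withdrawal it allows three different end dates (day 14, 28 or 56), so sites could apply it differently. For exposed pregnancies it misses most births, and it misses the birth whenever the patient leaves once the pregnancy is found.

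The size rests on two pouches a day, nominal visit dates and the assumed gestation. The number of patients is unknown (0 to 12 for the first path) and may be small. The change is still worth making: as written, the rule gives the wrong answer for foreseeable patients, and this is more than a missing detail.

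**What to change.** In section 13.4.2, replace the definition in parentheses with three provisions:

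- SAEs are collected until 2 weeks after the latest of the last dose, the last attended visit (scheduled, withdrawal or relapse follow-up) and the last contact.
- The date of last dose is recorded in the eCRF, and obtained by phone if the patient does not return.
- Any pregnancy with exposure to study product is reported to the sponsor and its outcome recorded, whatever the 2-week limit.

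For example, for a patient lost after the month-3 call (365.25 ÷ 4 ≈ day 91), the window would end no earlier than about day 91 + 14 = 105, where it now ends on day 14.

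The cost is a short amendment, one eCRF date and a few phone contacts. Data for patients who cannot be reached will still be missing. The SAP already describes enrolment in the past tense. If follow-up is complete, the study report should instead give last-dose dates and the actual length of SAE observation by arm.
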